## 5.2 Planned Enrollment

ANTICIPATED/PLANNED ENROLLMENT for ENTIRE STUDY: Number of Participants ( must provide exact numbers. i.e. no range )			
Ethnic Categories	Sex/Gender		
	Females	Males	Total
Hispanic or Latino	1,957	0	1,957
Not Hispanic or Latino	30,666	0	30,666
Ethnic Categories: Total of All Participants	32,623	0	32,623
Racial Categories			
American Indian/Alaska Native	391	0	391
Asian	3,720	0	3,720
Native Hawaiian or Other Pacific Islander	391	0	391
Black or African American	2,120	0	2,120
White	23,717	0	23,717
More Than One Race	2,283		2,283
Racial Categories: Total of All Participants	32,623	0	32,623

## 5.3 Analysis Plans

### 5.3.1 Analysis plan relevant to primary objectives 2.1 and secondary objective 2.2.1

Figure 1 provides an overview of how our outcomes will be defined by randomization arm.

We define **screening completion** as follows:

Direct Mail or Opt-In:

- a) Receive in-clinic screening; or
- b) Return kit and complete reflex cytology if recommended per USPSTF primary HPV guidelines.

Usual care or Education:

- a) Receiving in-clinic screening.

Screening completion is our primary outcome because of the importance of ensuring individuals follow through with a complete screening episode. One potential disadvantage of a self-collected test is the estimated 8% of individuals who have an other-HR HPV positive or unsatisfactory result who will need to have an in-clinic Pap to determine whether any additional diagnostic evaluation is needed (whereas with in-clinic primary HPV screening, the same sample is used for both HPV testing and reflex cervical cytology).

Screening initiation is a secondary outcome. We define **screening initiation** as either receiving in-clinic cervical cancer screening or returning an HPV self-sampling kit (without the requirement to complete reflex cytology when warranted). Screening initiation is an important indicator of the success or failure of self-collection, since returning an HPV self-sampling kit will count towards cervical cancer screening for Healthcare Effectiveness Data and Information Set quality metrics. If there is a large difference between initiation and completion, it will be informative for implementation efforts (e.g., additional resources may be needed to ensure that individuals with other-HR HPV positive or unsatisfactory kit results complete in-clinic reflex cytology).

All analyses will be stratified by screening history population (Adherent, Overdue, and Unknown). All analyses will be based on the intention to treat principle, with individuals analyzed by the outreach approach arm to which they were randomly assigned. We will first conduct an overall chi-square test to assess differences in observed screening rates among randomization groups. The primary analysis will use a modified Poisson regression modeling approach to estimate the relative risk of screening completion associated with Direct Mail, and Opt-In strategies relative to Education (as appropriate by screening history population). A binary indicator for screening completion within 6 months (yes/no), as defined above, will be the dependent variable. Models will be fit using generalized estimating equations with an independent working correlation structure and robust standard error estimation to account for correlation between participants paneled to the same primary care provider. Models will adjust for baseline characteristics that differ by randomization arm. Models for Overdue participants will also be adjusted for overdue duration (<3 years and  $\geq 3$  years). The analysis for the outcome of screening initiation will use the same methods. The primary analysis will not include the Usual Care group, but secondary analyses will include this group, and will estimate the relative risk of screening outcomes for Education, relative to Usual Care.

Delays in screening impact time in compliance with screening recommendations and can also impact cancer outcomes. Thus, our analysis will also assess the time it takes to complete screening, defined as the number of days between randomization and screening completion, as a secondary outcome. We will use Kaplan-Meier log-rank tests to compare time to screening completion by randomization arm, with follow-up time censored at 6 months for non-completers. Analyses will be stratified by screening history population (Adherent, Overdue, and Unknown).

Given the importance of in-clinic follow-up after a positive self-sampling result, data on implementation outcomes will be critical for informing sustainability and translation to other health care systems. We will report the proportion of participants who complete necessary in-clinic follow-up after an abnormal kit result (e.g., reflex cytology after kit result other-HR HPV positive, or diagnostic colposcopy after kit result HPV16/18+) within 6 months after randomization. We will summarize these proportions separately by randomization group (Direct Mail vs. Opt-In) and by prior screening behavior (Adherent, Overdue, and Unknown).

Screening method choice is another important secondary outcome among participants randomized to Opt-In and Direct Mail. We will report the proportion of participants choosing no screening, in-clinic screening, or HPV self-sampling kit. We will summarize these proportions separately by randomization group (Direct Mail vs. Opt-In) and by prior screening behavior (Adherent, Overdue, and Unknown).

Differences in rates of missing data across groups can result in biased estimates of intervention effects. We expect missingness to be minimal since outcome data on screening completion will be defined from automated databases. All randomized participants will be included in the primary analysis, regardless of duration of enrollment in the 6-month follow-up period. In this age group and because outcome assessment is based on only 6 months of post-randomization follow-up, loss to follow-up is expected to be minimal. We do not anticipate any effect of assigned treatment arm on health plan disenrollment. However, we will report the rate of disenrollment by arm. The primary analysis will be unweighted, but if disenrollment rates are high (>10%), we will also perform sensitivity analyses using follow-up duration as an offset parameter in the Poisson regression models. The offset parameter allows estimation of the screening completion rate for censored data where participants had varying lengths of follow-up time.

To protect against multiple comparisons for analyses among the screening-adherent population (which has 3 intervention groups in the primary analysis), we will use the Fisher protected least-significant difference approach, which requires that pairwise group comparisons are made only if the overall omnibus test of any differences between group is statistically significant. The referent group for all analyses will be Education. When evaluating Opt-In and Direct Mail, the primary interest is in the impact of the mailed-kit interventions. The educational materials may also impact screening rates, but by using Education as the referent group for comparisons, the estimated group differences will be the effect related to the mailed kit.

The secondary analysis comparison between Education and Usual Care will allow estimation of the effect of the educational materials alone.

Starting with recruitment wave 43, the original educational brochure was replaced with new brochures, revised based on focus group feedback. A new non-age-specific brochure, plus age-tailored ( $\leq 45$  and  $>45$  years of age) educational brochures were produced, and study participants, stratified by age group, were randomized to receive the non-age-specific or age-tailored materials. Using data from this embedded sub-study, we will investigate the effects of the revised education materials compared to usual care, and the effects of age-tailored materials compared to non-age-specific materials, on screening completion. This analysis will be limited to individuals randomized to the Usual Care or Education arms, starting with wave 43. We will use a generalized linear model approach, with log link function and Poisson error distribution to estimate the difference in screening completion rates. Indicators for usual care, non-age-specific materials, or age-tailored materials will be the exposure variables, and the binary outcome of screening completion (yes/no) will be the outcome. For the primary analysis, we will assume a constant effect of the revised education materials, and of age-tailoring, across all individuals, and the model will be fit using data from individuals in all screening history groups (Adherent, Overdue, and Unknown), and all ages. In secondary analyses, we will explore whether the effect of the non-age-specific and age-tailored materials differ by screening history or age ( $\leq 45$  and  $>45$ ) by adding indicator variables for these characteristics and interaction terms between these variables and the primary exposure variables.

Further analytic details of the above analyses, and additional secondary and exploratory analyses are provided in the study's Statistical Analysis Plan (SAP).

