## 5. STATISTICAL CONSIDERATIONS

### 5.1 Sample Size

[figure not shown]
Our sample size calculations are based on pairwise comparisons of screening rates and used preliminary data from the KPWA electronic medical record and observed data from the prior HOME trial. Using 2019 KPWA cervical cancer screening data, we estimate 37.1% of screening-adherent, 30.8% of Overdue, and 27.8% of individuals with Unknown screening histories will be screened within 6 months of randomization in the Education arm. Calculations assume a two-sided level 0.05 test, for differences in two proportions.

Our sample size was selected for adequate power to detect meaningful differences in cervical cancer screening rates between outreach strategies within each of the 3 target populations. Meaningful differences were selected based on estimates from the literature and observed data from the HOME trial. Small improvements in screening uptake are important, particularly if cost-effective and patient-centered; thus, the study is powered to detect relatively small differences between groups. Based on prior studies, we anticipate the Direct Mail strategy will have a greater impact on screening uptake than the Opt-In approach compared to Education; therefore, we have powered the study for a larger minimal detectable difference for the Direct Mail effect.

We estimated the sample size necessary to have 80% power to detect a 3% difference between Opt-In and Education and a 5% difference in screening completion between Direct Mail and Education. We anticipate that the Direct Mail strategy will have a larger impact on screening outcomes than the Opt-In approach, therefore we selected a larger detectable difference (and thus a smaller sample size needed)

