for the Direct Mail group. However, in the screening-adherent population, we computed the sample sizes needed for the 3% and 5% detectable differences respectively, and based the Education arm on the sample size necessary for the Education versus Opt-In comparison, which was larger than necessary for the Education versus Direct Mail comparison. Thus, we will have 80% power to detect a 4.1% difference for the Education vs. Direct Mail screening completion comparison. We selected sample size in the Usual Care group to detect a difference of 3.0% in screening completion between Usual Care and Education for the Screening-Adherent and Unknown populations. Given the smaller sample sizes in the intervention groups for the Overdue population, we were unable to achieve a least detectable difference (LDD) of 3.0% between Usual Care and Education. With a sample size of N=1398 in the Education group (based on an LDD of 3% for Education vs Direct Mail), we computed the detectable difference for a variety of sample sizes for the Usual Care group. We selected a sample size of N=5592 (4 Usual Care participants for each Education participant), because further increasing the Usual Care group led to diminishing improvements in LDD. This sample size yields a least detectable difference of 3.8%.

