### 5.3.2 Analysis plans relevant to secondary objective one (2.2.1)

We will conduct a cost-effectiveness analysis of the outreach approaches for in-home HPV self-sampling kits with the incremental cost-effectiveness ratio (ICER) defined as the incremental cost per incremental increase in number of individuals who successfully achieve cervical cancer screening completion as defined by our primary study outcome, which includes appropriate follow-up of other-HR HPV positive HPV self-sampling kit results. The primary economic outcome will be an ICER. For screening-adherent individuals, ICERs will reflect comparisons between a) Opt-In and Education, b) Direct Mail and Education, and c) Direct Mail and Opt-In with Opt-In as the reference strategy. For Overdue individuals, the ICER will compare Direct Mail to Education. For individuals with Unknown screening histories, the ICER will compare Opt-In to Education. Within each screening status group, we will also be able to generate an ICER for Education compared to Usual Care. The study design precludes a comprehensive ICER comparing a single strategy (or set of strategies) to Education or Usual Care across all participants. Costs and screening outcomes will be varied in univariate, multivariable, and/or probabilistic sensitivity analyses as appropriate in Excel-based and Stata-based programs. Discounting and inflation adjustments will not be applied to costs or outcomes because of the 6-month assessment period. The STEP study will allow us to inform the delivery system with screening uptake projections, screening strategy selection, and the relative cost implications of switching from in-clinic to in-home testing, which may differ by prior screening behavior.

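### Education vs Usual Care has no whole-trial estimate stratified by screening history, and the one pooled model, from wave 43 on, names no history term despite unequal allocation

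*Combined protocol and SAP*

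**What the plan says.** Protocol section 5.3.1 sets the rule for the main analysis: "All analyses will be stratified by screening history population (Adherent, Overdue, and Unknown)". The primary models compare Direct Mail and Opt-In with Education. Education vs Usual Care is a secondary analysis there, and section 5.1 calls it exploratory.

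Section 5.1 sized that contrast population by population. For Adherent and Unknown: "We selected sample size in the Usual Care group to detect a difference of 3.0% in screening completion between Usual Care and Education". For Overdue, "we were unable to achieve a least detectable difference (LDD) of 3.0% between Usual Care and Education", and 3.8 points was accepted with four Usual Care participants per Education participant.

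The embedded sub-study, also in section 5.3.1, works differently. It uses only the Usual Care and Education arms from wave 43 on, assumes constant effects of the revised materials and of age-tailoring, and "the model will be fit using data from individuals in all screening history groups (Adherent, Overdue, and Unknown), and all ages". The exposure variables named for its main model are indicators for usual care, non-age-specific and age-tailored materials. Indicators for screening history and age, with interaction terms, enter only in secondary analyses. The section refers further secondary and exploratory analyses to a separate SAP.

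**The concern.** Education vs Usual Care is the one contrast randomized in all three populations, with 21,854 planned participants. Three separate estimates leave unused the precision that a stratified combination would give. Section 5.1 itself says that small gains in uptake matter and that the Overdue population could not reach 3.0 points.

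The sub-study does combine the populations, but for the last part of recruitment only. It also raises a second problem. The allocation ratio differs by population and so does the expected completion rate, so a pooled model without history terms compares arms with different population mixes. Part of any Education effect it reports would reflect that mix.

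Finally, two statements in the same section disagree: one says every analysis is stratified by history, and the other pools over history.

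**Working it through.** **Inputs, all from section 5.1.** "Calculations assume a two-sided level 0.05 test, for differences in two proportions"; 80% power; and for the Education arm, "we estimate 37.1% of screening-adherent, 30.8% of Overdue, and 27.8% of individuals with Unknown screening histories will be screened within 6 months". Planned sizes:

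| Population | Education rate | Education n | Usual Care n | Usual Care:Education |
|---|---|---|---|---|
| Adherent | 37.1% | 4171 | 3879 | 0.93 |
| Overdue | 30.8% | 1398 | 5592 | 4.00 |
| Unknown | 27.8% | 3686 | 3128 | 0.85 |
| Total | | 9255 | 12,599 | |

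**1. The plan's own figures.** I solved the two-proportion power formula (pooled variance under the null, no continuity correction, Usual Care below Education) for the difference. It gives 2.99, 3.78 and 3.00 points, against the stated 3.0, 3.8 and 3.0. They reproduce.

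**2. Whole-trial stratified estimate.** The variance in each population is v = pE(1-pE)/nE + pU(1-pU)/nU, with a common 3-point effect (pU = pE - 0.03).

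- Adherent: SE 0.01067, 1/v = 8781
- Overdue: SE 0.01372, 1/v = 5309
- Unknown: SE 0.01068, 1/v = 8766

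Combined SE = 1/sqrt(8781 + 5309 + 8766) = 1/sqrt(22,856) = 0.00661. The detectable difference is (1.960 + 0.842) x 0.00661 = 1.85 points; Mantel-Haenszel weights give 1.86. Power for a common 2-point effect is 85%, against 46%, 31% and 46% within the populations.

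The planned models estimate relative risks. On the log scale the SEs are 0.0301, 0.0455 and 0.0409, and 0.0214 combined. The gain over the best single population is therefore 1 - 0.0214/0.0301 = 29%, compared with 1 - 0.661/1.067 = 38% for risk differences.

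**3. By brochure period.** The brochure changed at wave 43. The number of waves is an assumption: targets divided by weekly samples give 13,735/231 = 59.5, 8388/142 = 59.1 and 10,500/177 = 59.3, so about 60. (For Unknown I used the sum of the weekly arm counts, 53 + 62 + 62 = 177.) Waves 1-42 are then 70% of recruitment and the rest 30%:

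- waves 1-42: 1.85/sqrt(0.7) = 2.2 points
- wave 43 on: 1.85/sqrt(0.3) = 3.4 points (SE 0.66/sqrt(0.3) = 1.2)

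Using the weekly arm counts directly, 16 to 20 waves after the change give 3.6 to 3.2 points.

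**4. Crude pooling with no true effect.** Apply each population's Education rate to both arms:

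- Education: (4171 x 0.371 + 1398 x 0.308 + 3686 x 0.278)/9255 = 3002.7/9255 = 32.44%
- Usual Care: (3879 x 0.371 + 5592 x 0.308 + 3128 x 0.278)/12,599 = 4031.0/12,599 = 31.99%

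The difference is +0.45 points, RR 1.014. The weekly counts that apply from wave 43 (156 Education, 212 Usual Care) give the same: 50.60/156 = 32.43% vs 67.80/212 = 31.98%.

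Over 18 waves (2808 vs 3816) the crude SE is sqrt(0.2191/2808 + 0.2175/3816) = 0.0116, so the shift is 0.45/1.16 = 0.39 SE. A nominal 5% two-sided test would then reject in about P(Z > 1.57) + P(Z > 2.35) = 5.8% + 0.9% = 6.7% of null trials.

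Age-tailored vs non-age-specific materials is not affected in this way, because that allocation is 1:1 within each randomization group.

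**5. History-by-arm contrasts for the kits.** The SE is the root of the summed variances.

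- Opt-In, Adherent vs Unknown: sqrt(0.01066² + 0.01060²) = 0.0150, detectable 4.2 points
- Direct Mail, Adherent vs Overdue: sqrt(0.01473² + 0.01780²) = 0.0231, detectable 6.5 points

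**The case against.** The design is deliberately population-specific. The primary objective is stratified by prior screening behavior, and section 5.1 powers the outreach comparisons within each population, for instance "We estimated the sample size necessary to have 80% power to detect a 3% difference between Opt-In and Education". Opt-In and Direct Mail each exist in only two populations. Education vs Usual Care is secondary or exploratory, and section 5.1 allows its Usual Care sample to be cut. The sub-study already pools over history and explores history interactions. The 1.85-point figure spans two brochure generations; reported by period, the only new estimate is for waves 1-42, and it concerns a brochure since replaced. The separate SAP may already contain such an analysis.

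Most of this stands, and it limits the point to an addition beside the planned analyses. It does not answer the missing history term: a constant effect across populations is a different assumption from equal completion rates across populations, and the plan's own rates differ.

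Two stronger readings are tempting, and the documents support neither:

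- A reader might infer that the kit contrasts also lose precision. They do not. Their targets are population-specific, their sizes were set for those targets, and an interaction test would add no precision.
- A reader might infer that the plan will claim different effects in different populations without a test. No section plans such a claim. Section 5.3.2 says only that what the delivery system learns, including cost implications, "which may differ by prior screening behavior". A kit interaction test would detect only 4.2 or 6.5 points, more than the 3- and 5-point design effects, so a null result would say little.

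**Conclusion.** The point holds for Education vs Usual Care only. The main analysis gives it no estimate combined over screening history. The one pooled comparison covers wave 43 onward, and as written its main model leaves a mix imbalance worth about +0.45 points in favor of Education. That is small but avoidable, and it bears on the comparison of revised materials with Usual Care.

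The gain from a history-adjusted estimate is moderate: about 2.2 points detectable for the first brochure. The 3.4 points from wave 43 on is no sharper than the whole-trial figure in Adherent or Unknown, so for that period the benefit is the adjustment. The 1.85 points applies only if both brochure periods are combined.

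These sizes rest on the planned rates and numbers, about 60 weekly waves, a common effect across populations, and no allowance for provider clustering (the plan's own calculation makes none). The absence of these analyses is established for the protocol text only, because the separate SAP could not be checked.

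**What to change.** 1. Keep the stratum-specific models as they are.
2. Add one supplementary modified Poisson GEE for Education vs Usual Care, with screening-history main effects and robust standard errors clustered on primary care provider. Report it for waves 1-42 and for wave 43 onward; label any figure combining the two as an average over brochures.
3. Add the same screening-history main effects to the main sub-study model.
4. Reword the general statement on stratification so that it excepts the sub-study and the new model.
5. Optionally, give history-by-arm estimates with intervals for the kit contrasts, labelled descriptive.

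The cost is a few lines of text and one or two models on data already collected. The downside is that the overall estimate averages three populations for a secondary contrast, so it belongs beside the stratum results and cannot replace them. If the separate SAP already specifies items 2 and 3, a cross-reference is enough. The additions should be fixed while the scientific leadership is still blinded to outcomes under section 7.4.

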### 1.2 Rationale

Pap screening has reduced cervical cancer incidence and mortality by >50% over the last 40 years. Nearly all cervical cancer can be prevented by identifying and removing precancers caused by high-risk HPV. However, US adherence to guideline-recommended screening intervals has declined from a high of 82% in 2003 to 74% in 2016. *Increasing screening coverage is a top national priority for cervical cancer prevention.* Well-documented barriers include sociodemographic factors (e.g., race and ethnicity and insurance), knowledge about HPV and cervical cancer, beliefs about importance of regular screening, discomfort/embarrassment with the Pap procedure, and scheduling/time barriers. Individuals who never or rarely screen are a clear intervention priority, as >50% of the 12,000 cervical cancers diagnosed annually are in people who have not been recently screened. At the same time, keeping people engaged in routine screening is critical; in 2017, only 48% of KPWA individuals who were up-to-date with Pap testing attended screening within 6 months after their next due date. HPV vaccinations will not end the need for cervical cancer screening, since current vaccines do not protect against all cancer-associated HPV types. Identifying new, patient-centered options that motivate continued screening initiation and completion is essential now and in the future.

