## **4. STUDY PROCEDURES**

### **4.1 Subject Recruitment and Screening**

#### **4.1.1 Primary objective (2.1), and secondary objective (2.2.1)**

Under a waiver of consent and HIPAA authorization, the study programmer will use electronic medical record data from KPWA to identify individuals who are due for cervical cancer screening based on previous screening history:

- 1) *Screening-adherent and coming due* (previously screened and due for screening within three months);
- 2) *Overdue* (never screened; or HPV and Pap co-test >5.25 years ago [or Pap alone >3.25 years ago]; or no past Pap and continuously enrolled at KPWA for ≥3.25 years)\*; and
- 3) *Unknown Prior Screening* (enrolled ≥6 months and <3.25 years, with no recorded screening history).

[figure not shown]
\*Individuals with due dates falling between March 2020-August 2020 will have randomization delayed for 12 months (March 2021-August 2021), because KPWA halted routine cervical cancer screening during these months of the COVID-19 pandemic. A 12-month delay in randomization of these individuals will (1) allow time for the delivery system to catch-up on the 6-month back log of screening visits, and (2) avoid potential misclassification of individuals as overdue solely due to their temporary inability to screen during the halted screening or due to their potential likely difficulty to schedule a screening visit during the expected surge in catch-up visits.

Clinical outreach provided by KPWA includes sending individuals a reminder letter that they are coming due approximately 60 days before their screening due date (for screening-adherent individuals), or repeat reminders every 60 days for individuals who are overdue (known to be overdue, or with an unknown screening history). The study programmer will use these clinical system outreach letters to identify eligible individuals. Each week, we will identify individuals who meet eligibility criteria and are mailed a clinical outreach letter. Eligible individuals will be identified, and a random sample will be randomized to intervention groups, stratified by screening history, as described below. Randomization will occur weekly over a 14-month recruitment period, and eligible individuals will be enrolled under a waiver of consent.

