The study programmer will use SAS software built in simple random sample procedure to randomly select study participants from all eligible individuals, and then randomly allocate participants into Usual Care, Education, or 1 of 2 intervention arms based on prior screening history (See Figure 1). *Screening-adherent* individuals will be randomized to one of 4 arms: Usual Care, Education, Opt-In or Direct Mail. *Overdue* individuals will be randomized to Usual Care, Education, or Direct Mail. *Unknown* individuals will be randomized to Usual Care, Education, or Opt-In. Target sample size estimates are detailed in section 5.1. During study enrollment and follow-up, the electronic randomization sequence will be concealed from all researchers by the study programmer, and allocation will only be revealed as minimally necessary to investigators directly involved in data collection and/or safety monitoring.

In March 2021, investigators decided to embed a sub-study to investigate the impact of age-tailored educational materials on screening uptake. The initial wave/week 1-42 educational materials were reviewed and edited via supplemental PATH study grant funding (P50 CA244432). The materials were studied via focus groups conducted by the PATH research group, results were reviewed and brochures edited by the PATH and STEP study teams, and new non-age-specific "optimized"/edited and age-tailored ( $\leq 45$  and  $>45$  years of age) educational brochures were produced. The sub-study will be implemented from wave/week 43 onward. Individuals randomized to study intervention arms will be stratified by  $\leq 45$  versus  $>45$  years of age, and then randomly allocated 1:1 to either age-tailored or non-age-tailored educational materials (see Figure 2). The study programmer will use the same randomization and concealment procedures for the sub-study stratification and allocation.

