#### 4.2.3 Medical records data

We will obtain data from subject electronic medical records including cervical cancer screening/diagnostic/treatment, medical information related to cervical cancer risk factors, health care use (including preventive services), comorbidities and demographic information.

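### The primary models pick covariates by chance imbalance between randomized arms; a short prognostic list should be fixed before outcomes are unblinded

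*Combined protocol and SAP*

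**What the plan says.** Section 5.3.1 makes modified Poisson regression the primary analysis, with Education as referent, fitted separately in the Adherent, Overdue and Unknown populations. Its covariate rule is one sentence: "Models will adjust for baseline characteristics that differ by randomization arm". It adds one named term for one population: "Models for Overdue participants will also be adjusted for overdue duration", split at 3 years. Screening initiation is analyzed the same way.

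The text gives no candidate variables, no test and no threshold for what counts as differing. It does not say whether Usual Care, which is left out of the primary analysis, counts in that comparison. The candidate pool in Section 4.2.3 is broad: "medical information related to cervical cancer risk factors, health care use (including preventive services), comorbidities and demographic information".

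Section 4.1.1 says the study programmer will select participants at random and "then randomly allocate participants into Usual Care, Education, or 1 of 2 intervention arms based on prior screening history". Section 5.1 fixes the weekly number per arm within each population. Section 5.3.1 also says: "Further analytic details of the above analyses, and additional secondary and exploratory analyses are provided in the" study's SAP. That SAP was not part of the text available for this review.

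**The concern.** With random allocation, baseline differences between arms carry no information about which variables predict screening. Choosing covariates on that basis has two consequences.

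- The primary model cannot be written down until baseline data are compared by arm. Because the criterion is unstated, two competent analysts could fit different models and report different relative risks.
- A strong predictor of screening is no more likely to enter than noise, so the precision that adjustment can give is mostly lost.

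Overdue duration is the one covariate fixed in advance. Screening history is handled by stratification, and calendar time by the constant weekly allocation. The Adherent and Unknown models have no fixed covariate. At stake is the adjusted relative risk for every kit comparison, in a trial powered for differences of 3 to 5 percentage points.

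**Working it through.** **1. The plan's own figures.** Section 5.1 uses a two-sided 0.05 test of two proportions with 80% power. No stated figure depends on the covariate rule, so this step only confirms the setting for the simulations. Per arm, n = [1.960·√(2p̄q̄) + 0.842·√(p₀q₀ + p₁q₁)]² / (p₁ − p₀)².

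| Comparison with Education | Rates | n | n, continuity-corrected | Stated |
|---|---|---|---|---|
| Adherent, Opt-In | 37.1% v 40.1% | 4133 | 4200 | 4171 |
| Adherent, Direct Mail | 37.1% v 42.1% | 1501 | 1541 | 1514 |
| Overdue, Direct Mail | 30.8% v 35.8% | 1394 | 1434 | 1398 |
| Unknown, Opt-In | 27.8% v 30.8% | 3612 | 3679 | 3686 |

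All agree within 3%.

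**2. How often the rule changes the model.** The number of candidates, k, is assumed to be 5 to 20, and candidates are taken as independent.

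- If the criterion is p<0.05, P(at least one flagged) = 1 − 0.95^k. This is 0.226 for k=5, 0.401 for k=10 and 0.642 for k=20. With 10 candidates in each of three populations, the chance that at least one primary model changes is 1 − 0.95^30 = 79%.
- If the criterion is a standardized difference above 0.1, the chance per covariate is 2·[1 − Φ(0.1/√(1/n₁ + 1/n₀))]:
  - Overdue (1398 v 1398): 0.0082, so 4.0-15.2% for k = 5 to 20.
  - Adherent (4171 v 4171 and 1514 v 4171): 0.000005 and 0.00086, so 0.4-1.7%.
  - Unknown (3686 v 3686): 0.000018, so under 0.1%.

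Two ordinary readings of one word thus give very different chances of an adjusted model.

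**3. Precision and error rates, first simulation.** There were 1,500 trials per setting, two arms, modified Poisson with robust standard errors and no provider clustering. The settings were Overdue (1398 per arm, 30.8%, +5 points) and Unknown (3686 per arm, 27.8%, +3 points). Fifteen independent binary candidates (prevalence 30%) were assumed, three of them prognostic.

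| RR of each predictor | SE reduction, fixed list | Equivalent extra participants | Power, p<0.05 rule → fixed list (Overdue; Unknown) |
|---|---|---|---|
| 1.2 | 0.4-0.6% | about 1% | 79.4→79.5; 81.7→82.4 |
| 1.35 | 1.2-1.6% | about 3% | 77.8→78.4; 79.7→80.7 |
| 1.5 | 2.3-3.0% | 5-6% | 80.0→81.2; 80.5→82.2 |

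The third column is (SE ratio)² − 1; for example 1/0.97² − 1 = 6.3%. Under the p<0.05 rule at least one true predictor entered in only 14-16% of trials; theory gives 1 − 0.95³ = 14.3%. Type I error was 4.0-5.5% under the rule and 3.8-5.9% with the fixed list. Monte Carlo standard errors are about 1 point for power and 0.6 for type I error.

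**4. Second simulation, different structure.** This used the Overdue setting, 2,000 trials, 10 candidates with 4 prognostic, jointly explaining about 2%, 5% or 9% of outcome variance. Power with no adjustment, the p<0.05 rule and the fixed list was 80.9/80.7/81.3%, 79.5/79.8/81.1% and 80.6/80.4/82.8%. The mean standard error of the log relative risk fell from 0.0538 to 0.0532, 0.0538 to 0.0527 and 0.0537 to 0.0516 (rule to fixed list), about 1% to 4%. Against no adjustment the rule gained essentially nothing. Type I error was 4.4-5.0% throughout.

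**5. Effect of the unstated criterion.** In the first simulation four readings were compared: nothing flagged, p<0.05, p<0.10, and standardized difference above 0.1. At the design effects the 5% significance verdict changed between readings in 1.6-2.9% of trials. Picking the most favorable reading gave type I error of 4.5-6.1%, an addition of 0.1-0.7 points.

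**6. Overdue duration.** Section 4.1.1 counts as Overdue people never screened, and those with "no past Pap and continuously enrolled at KPWA" for at least 3.25 years. Section 5.3.1 splits duration at 3 years without saying how they are coded, yet also says: "All randomized participants will be included in the primary analysis". An enrollment-based duration is possible, but the choice is not stated.

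**The case against.** The strongest objection is the unseen SAP: a covariate list or a definition of the criterion would normally sit there. That stands as a limit on what can be concluded about the whole plan. It does not remove the protocol sentence, which states a selection rule rather than leaving a blank.

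Second, the effect is small. This is correct: power gains are partly within Monte Carlo error, the largest need strong assumed predictors, and alpha is not inflated.

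Third, the overall chi-square test on observed rates uses no covariates, and in the Adherent population it gates the pairwise comparisons. True, but it does not produce the primary relative risks.

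Fourth, Section 7.4 keeps the scientific leadership blinded to outcomes until 6 months after the last enrollment, and choosing a favorable reading requires outcomes. This reduces the concern, but nothing says that covariates will be settled before that point.

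Fifth, the simulations omit provider clustering, the three-arm Adherent comparison and the overdue-duration term, and correlated candidates would lower the flagging rates. These limit how exact the figures are. The direction does not depend on them.

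Sixth, on the remedy: preventive-service history is short for some Unknown members, who may have been enrolled only 6 months, and insurance may predict little among current enrollees. That is a fair caution about which variables to name. Finally, the protocol's summary of changes mentions capturing screening history back to the enrollment date. This favors an enrollment-based duration but does not state the coding.

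**Conclusion.** The concern holds. As written, the primary adjusted relative risk in each population depends on chance imbalances judged by an undefined criterion, and predictors other than overdue duration enter only by luck. The practical size is modest: standard errors about 0.4-4% larger than a fixed prognostic list would give, 0.1 to about 2.5 points of power forgone, and no type I inflation when the rule is applied mechanically. These figures rest on assumed numbers and strengths of independent covariates, since the documents give none, and on models without provider clustering. The case for change is mainly prespecification of the primary estimate, with precision as a small bonus. The sponsor should make the change because it costs almost nothing; the trial is not invalid without it.

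**What to change.** Before outcomes are unblinded, replace the sentence in Section 5.3.1 with one short covariate list, used in all three populations whether or not the arms differ.

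- Choose the list for prognostic value from the medical-record data. Examples are age, prior preventive-service use (over a look-back that all members of the population have), race and ethnicity, and insurance if available. Section 1.2 names the last two as screening barriers.
- Code unrecorded values as their own level, so that every randomized participant stays in the model.
- Keep overdue duration for the Overdue population, and state whether people with no prior screen on record form a separate level or get an enrollment-based duration.
- Report the unadjusted relative risk beside the adjusted one, and use the baseline table for description only.
- If the SAP already fixes the covariates, amend Section 5.3.1 to match it.

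The cost is two or three sentences. Section 4.2.3 already plans to obtain these kinds of data, and a few extra model terms are negligible with at least 1,398 participants per arm.
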